### **12-Lead ECGs**

12-Lead ECGs will be performed in screening, prior to procedure (baseline), at the completion of procedure, prior to hospital discharge, and at one, three, six, and 12 months post-procedure. The number and percent of subjects with each ECG rhythm will be reported by time point.

### **24-Hour Holter Monitor**

A 24-Hour Holter monitor of heart rhythm will be completed at three, six, nine, and 12 months. The number and percent of subjects with each heart rhythm will be reported by time point. The Holter data will be listed along with the 12-Lead ECG data.

### **Physical Exam Findings**

Physical exams will be performed at screening (baseline), pre-procedure, discharge, and at the one, three, six, and 12 month follow up visits. A physical exam shift table will be constructed for each post-procedure time point in order to count the frequency of each shift for each body system. Shifts include normal/normal, normal/abnormal, abnormal/normal, and abnormal/abnormal.

### **Vital Signs**

Vital signs will include heart rate, blood pressure, and temperature. Vital signs will be taken at screening (baseline), discharge, and at the one, three, six, and 12 month follow up visits. For each vital sign, summary statistics (mean, standard deviation, median, range, n) on the raw as well as their changes from baseline will be presented by timepoint. If repeat vital signs are taken at a given time point, then the last measurement will be used for the analysis tables. All vital signs will be listed.

## 5.0 Analysis of Effectiveness

### 5.1 Description of Effectiveness Objectives

#### 5.1.1 Description of Primary Effectiveness Objective

The primary objective of this study is categorized as a safety measure (see Section 4.1.1). All effectiveness objectives are considered to be secondary and are described in Section 5.1.2.

#### 5.1.2 Description of Secondary Effectiveness Objectives

Secondary measurable effectiveness objectives include the following, which are divided into procedure outcome measures and clinical outcome measures.

The **procedure outcome measures** are:

- Proportion of subjects with acute procedural (ablation) success defined as:
  - Conversion to sinus rhythm (with or without direct current cardioversion [DCCV]) within 12 hours of the procedure
  - Procedural conversion to atrial flutter, atrial tachycardia or other organized supraventricular rhythm
- Procedure fluoroscopy time
- Ablation time to complete PVI
- Ablation time for non-PVI ablation
- Ablation time for right atrial ablation
- Number of DCCV completed during the procedure

The **clinical outcome measures** are:

- Proportion of subjects with freedom from documented episodes of AF/AT/AFL lasting longer than 30 seconds, based on the 24-hour continuous ECG monitor at three, six, nine, and 12 months post ablation. Analysis will include:
  - Freedom from AF/AT/AFL without AADs
  - Freedom from AF/AT/AFL with AADs
  - Freedom from AF/AT/AFL with a single procedure
  - Freedom from AF/AT/AFL with multiple procedures
- Improvement of left atrial (LA) size at 12 months compared to baseline
- Number of repeat ablation procedures in follow-up period from day 91-270 (i.e., from three months to nine months)
- Number of DCCV in first 90 days post-ablation
- Number of DCCV from day 91-365 (i.e., from three months to 12 months)
- Changes in patient reported outcomes (PROs) in the follow-up period, based on the AFEQT questionnaire

## 5.2 Analysis of Effectiveness Objectives

### 5.2.1 Analysis of Primary Effectiveness Objective

N/A

### 5.2.2 Analysis of Secondary Effectiveness Objectives

All secondary effectiveness analyses will be conducted on the treatment population.

#### Procedure Outcome Measures

The continuous procedure outcome measures, which include procedure fluoroscopy time, ablation time to complete PVI, ablation time for non-PVI ablation, ablation time for right atrial ablation, and the number of DCCV completed during the procedure will be summarized via mean, standard deviation, median, range, and number of non-missing responses. Ninety-five percent (95%) confidence intervals (CIs) on the mean will also be provided.

The categorical procedure outcome measure of acute procedural success will be summarized by the number of successful subjects and the proportion of successful subjects. An exact binomial 95% CI on the proportion will also be provided.

#### Clinical Outcome Measures

The number and proportion of subjects with freedom from documented episodes of AF/AT/AFL lasting longer than 30 seconds, based on the 24-hour continuous ECG monitor at three, six, nine, and 12 months post ablation will be displayed, along with exact binomial 95% CI's for each proportion. Separate proportions and confidence intervals will be calculated for:

- Freedom from AF/AT/AFL with a single procedure
- Freedom from AF/AT/AFL with a single procedure without AADs
- Freedom from AF/AT/AFL with a single procedure with AADs
- Freedom from AF/AT/AFL with multiple procedures
- Freedom from AF/AT/AFL with multiple procedures without AADs
- Freedom from AF/AT/AFL with multiple procedures with AADs.
- Freedom from AF with a single procedure
- Freedom from AF with a single procedure without AADs
- Freedom from AF with a single procedure with AADs
- Freedom from AF with multiple procedures
- Freedom from AF with multiple procedures without AADs
- Freedom from AF with multiple procedures with AADs.

Descriptive statistics (mean, standard deviation, median, range, and number of non-missing responses) on the raw and change from baseline (CFB) LA size will be reported

at 12 months, along with a separate set of descriptive statistics for the raw baseline data. A 95% CI on the mean will also be provided.

The number of repeat ablation procedures in follow-up period from day 91-270 (i.e., from three months to nine months) will be summarized via mean, standard deviation, median, range, and number of non-missing responses. A 95% CI on the mean will also be provided.

The number of DCCV in first 90 days post-ablation and the number of DCCV from day 91-365 (i.e., from three months to 12 months) will be summarized via mean, standard deviation, median, range, and number of non-missing responses. A 95% CI on the mean will also be provided.

Raw and CFB scores for the AFEQT questionnaire will be computed and summarized with descriptive statistics (mean, standard deviation, median, range, and number of non-missing responses) by time point (one, three, six, and 12 months post ablation). The overall AFEQT score is calculated according the following formula:

$$AFEQT_{\text{Overall}} = 100 \times \left( 1 - \frac{\sum A_j - n}{6n} \right),$$

where the summation extends over all items with a response, *excluding questions 19 and 20*, and  $n$  represents the number items with responses. Items lacking responses are dropped from the analysis. If all items are missing, then the overall score is also missing.

This analysis will be performed for the overall score and its three subscales (symptoms, daily activities, and treatment concern) and for the separate treatment satisfaction score. The subscale scores are computed similarly on the following subsets of questionnaire items:

Subscale	Questionnaire items included
Symptoms	1, 2, 3, 4
Daily Activities	5, 6, 7, 8, 9, 10, 11, 12
Treatment Concerns	13, 14, 15, 16, 17, 18

As in the overall score, missing items are dropped from the analysis. If all items in a subscale are missing, the subscale score is also missing.

As noted above, items 19 and 20 are *not* included in the overall AFEQT score. These items form a separate scale for treatment satisfaction:

$$AFEQT_{\text{Treatment Satisfaction}} = 100 \times \left( 1 - \frac{A_{19} + A_{20} - n}{6n} \right),$$

where  $n$  is the number of items answered.

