### Clinical Outcome Measures

- Analysis at 3, 6, 9, and 12 months post ablation (with a 24 hour continuous ECG monitor) of the proportion of subjects with freedom from documented episodes of AF lasting longer than 30 seconds. Analysis will include:
  - Freedom from AF/AT/AFL without AADs
  - Freedom from AF/AT/AFL with AADs
  - Freedom from AF/AT/AFL with a single procedure
  - Freedom from AF/AT/AFL with multiple procedures

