#### Arrhythmia Recurrence beyond the Blanking Period

Development of AF/AFL/AT beyond the blanking period should first be documented with an ECG or a 24-hour continuous ECG monitor. Recurrence of an arrhythmia will be recorded on the eCRF as part of the continued management process of the subject in follow-up. These will be documented at unscheduled or routine (three-, six- and twelve-month) follow up visits.

Treatment should follow the Investigator's standard of care and may include DCCV, AAD administration or repeat ablation (retreatment procedure). Use of a DCCV is recommended prior to an ablation as many of these arrhythmias may be self-limited. One retreatment is allowed and may only occur in the time range from day 91 through day 270 post-ablation.

In a retreatment procedure, the AcQMap System should be used following the same protocol as the index procedure. Documentation of the retreatment will be on the procedure retreatment eCRF form. Follow-up visits will restart using the same schedule as with the index procedure (7-day call, 1, 3, 6 months); however, the study completion date (12 months from the index procedure) will not change.

[figure not shown]
**Hospital admissions and clinic visits to treat these arrhythmias (cardioversion, in-patient medication change and ablation) will not constitute an SAE but will be reported as an additional intervention to the management of the persistent AF.** In the event the subject suffers an untoward or unanticipated complication as a result of the arrhythmia (i.e. thrombotic event, pulmonary edema etc.), an adverse event reporting will occur and be adjudicated by the Clinical Events Committee in accordance with the CEC Charter.

Screening, procedure and follow-up visits are outlined in Table 2 and a flow diagram of visits is pictured in Figure 10.

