**STATKING Clinical Services**

## Revision History

### Version 1.1 to 2.0

1. Listing 6 (AEs): modified to add columns specifying device relationship to AE for each device.
2. Listing 15 (Catheter Data): Part 5 header corrected. Part 4 Sheath Model number and Lot number added.
3. Listing 16 (PVI Data): Column added to identify visit and PVI count.
4. Table 2 and Time-to-event specification: TTE defined as  $TTE = \text{End-Date} - \text{Start-Date}$  rather than  $\text{End-Date} - \text{Start-Date} + 1$ .
5. Tables 7 and 35: Footnote added to state data source as continuous monitor data with 12 lead imputation when continuous monitor data are unavailable.
6. Table 16: Highest Relationship to Device expanded to summarize relationships to System, Catheter, Sheath, and PEK (in accord with added tables 20- 22).
7. Tables 16, 17, 18, 19 (AEs): Table sources modified to use CEC adjudication only, titles changed to reflect this. Text of Section 4.2.2 changed to reflect these changes.
8. Table 19 (AE Relationship to Device) – Changed to Relationship to AcQMap Catheter.
9. Tables 20-22 – Added to summarize additional AE relationship assessments.

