## 2.3 Missing Data Conventions

With the exceptions noted below, no missing value imputation will be used. That is, all analyses will be based on the observed data (i.e., complete case analysis).

Missing 24-hour Holter rhythm data will be imputed from 12-lead ECG results for the corresponding visit at 3, 6, and 12 months. Statistics will be computed for complete case analysis and with the imputed data present.

In case of missing data for dates, January will be imputed for missing months and the first will be imputed for missing days for purposes of elapsed time computations.

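### Freedom from documented AF/AT/AFL is scored only at scheduled recordings, so a recurrence documented and cardioverted between them can leave a subject counted as free

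*Combined protocol and SAP*

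**What the plan says.** SAP section 5.1.2 defines the outcome as "Proportion of subjects with freedom from documented episodes of AF/AT/AFL lasting longer than 30 seconds" and ties it to the scheduled monitor. SAP section 5.2.2 repeats the tie: the proportions, "based on the 24-hour continuous ECG monitor at three, six, nine, and 12 months post ablation will be displayed". Protocol section 6.2.2 has the same source: "Analysis at 3, 6, 9, and 12 months post ablation (with a 24 hour continuous ECG monitor) of the proportion of subjects".

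One substitute is allowed. SAP section 2.3 states: "Missing 24-hour Holter rhythm data will be imputed from 12-lead ECG results for the corresponding visit at 3, 6, and 12 months". There is none at month 9. The SAP revision history, version 1.1 to 2.0, describes a footnote to the result tables that names the same sources: "Footnote added to state data source as continuous monitor data with 12 lead imputation when continuous monitor data are unavailable".

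Protocol section 7.5 is wider on how a recurrence comes to be documented: "Development of AF/AFL/AT beyond the blanking period should first be documented with an ECG or a 24-hour continuous ECG monitor". It adds: "These will be documented at unscheduled or routine (three-, six- and twelve-month) follow up visits". Those records go to the eCRF as part of managing the subject. SAP section 5.2.2 summarises the number of DCCVs on day 91-365 as a separate count (mean, SD, median, range).

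The supplied text does not say that an unscheduled ECG or a DCCV after day 90 makes a subject a failure. It also does not say whether a failed recording at one time point carries forward to the next.

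**The concern.** The name of the outcome suggests that any documented recurrence counts. The scoring rule looks only at fixed recordings. Protocol section 7.5 recommends DCCV before a repeat ablation, so documentation at an unscheduled visit followed by cardioversion is a foreseeable path. Such a subject may be in sinus rhythm at the next recording. A DCCV does not move the subject between the single- and multiple-procedure rows or between the rows with and without AADs. Because DCCVs appear only as a mean and range, a reader cannot tell how many subjects counted as free had been cardioverted.

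What is at stake is the meaning of the reported 6- and 12-month figures. Protocol section 5.2 calls freedom from AF at those times treatment success and says that comparison with literature controls may offer insight. The synopsis foresees publication at both times.

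**Working it through.** **The plan's own figure.** The documents give no expected rate for this outcome. Their only computed figure is N = 125 for the 24-hour safety endpoint. An observed 120/125 gives a Clopper-Pearson 95% interval of 90.91% to 98.69%, a half-width of 3.888%, which matches the stated 3.89%. It reproduces, and nothing below changes it.

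**Following the rule for one subject.** Take 3, 6, 9 and 12 months as days 90, 180, 270 and 365 (an assumption). With the windows in protocol Table 2, the 3-month window closes on day 90 + 14 = 104 and the 6-month window opens on day 180 - 30 = 150. Suppose AF is documented on an ECG at an unscheduled visit between day 105 and day 149 and is cardioverted, there is no repeat ablation, and the 6-, 9- and 12-month monitors are clean.

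- Protocol 7.5: a documented recurrence after blanking.
- SAP 5.2.2, freedom rows: free at 6, 9 and 12 months.
- SAP 5.2.2, DCCV summary: adds one to the day 91-365 count.

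**Effect per subject.** Each such subject adds 1/n to the reported proportion: 1/125 = 0.8 points. If only 110 or 100 are assessed (assumed), it is 0.9 or 1.0 points. Purely as illustration, 5 or 10 such subjects of 125 would add 4.0 or 8.0 points. The documents give no basis for choosing a number.

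**Chance that a scheduled recording meets an episode.** Assume one episode of L days, its start uniform over days 91-365 (365 - 90 = 275 days), and one-day recordings on days 180, 270 and 365. A recording on day m meets the episode if the start lies from m - L + 1 to m, which is L start days. For L up to 90 these sets do not overlap and lie inside the period, so the share is 3L/275.

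| L (days) | 3L/275 | Share met |
|---|---|---|
| 1 | 3/275 | 1.1% |
| 7 | 21/275 | 7.6% |
| 30 | 90/275 | 32.7% |
| 60 | 180/275 | 65.5% |
| 90 | 270/275 | 98.2% |

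Counting in continuous time gives 1.8%, 8.4%, 33.6% and 66.4% for 1, 7, 30 and 60 days, so the pattern does not depend on the day-counting convention. Short episodes that are promptly converted are mostly unseen; long ones are mostly seen.

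**Direction.** Ignoring a between-visit failure can only raise the proportion counted as free. The timing of recordings can work the other way. A 6-month monitor on day 205 (window: days 150-210) showing AF that began on day 200 is a failure at that visit, although the subject was free through day 180. The direction is therefore likely upward, not guaranteed.

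**The case against.** The strongest defence is that a fixed schedule is a legitimate choice. It examines every subject at the same times and avoids detection that depends on symptoms and site practice. The definition names the monitor openly, the table footnote states the source, and post-blanking DCCVs and day 91-270 repeat ablations are reported elsewhere. The outcome is secondary, SAP section 2.1 rules out hypothesis tests, and protocol section 5.2 says that clinical outcomes will not be used to imply effective lesion creation. All of this stands. It is why the scheduled-monitor result should stay and why the request is for a supplement.

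A reader might also infer more than the documents support:

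- *That between-visit recurrences never count.* One still present at a scheduled recording is counted there. Repeat ablation or an AAD may move a subject to another row. On the day conventions above, the 3-, 6- and 12-month windows cover 14 + 61 + 31 = 106 of the 275 post-blanking days (39%), and the text does not say which record is used when several fall in one window.
- *That recording 3 of 275 days (1.1%) means nearly all recurrences are missed.* That is time coverage. The chance of meeting an episode depends on its length, as the table shows.
- *That the reported figure must equal or exceed cumulative freedom.* The day-205 example shows otherwise.
- *That no scoring rule exists anywhere.* The Appendix B shells and the image of Figure 2 were not available. A list under protocol Table 2 groups subjects by DCCV, AAD or repeat ablation beyond blanking, but nothing shows that it is a scoring rule.

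**Conclusion.** The point holds in this form: on the supplied text, the scheduled recording or its same-visit ECG substitute is the only source for the freedom outcome, and a recurrence documented and cardioverted between recordings can leave the subject counted as free. For the single-procedure rows the likely effect is upward, by 0.8 points per affected subject if 125 are assessed. How many are affected cannot be derived from the documents. The detection shares rest on one episode per subject, a uniform start and nominal recording days. The conclusion is subject to whatever Appendix B or Figure 2 may contain. It does not touch the primary safety objective or the sample size. It is a worthwhile, inexpensive improvement to a secondary descriptive outcome, and does not invalidate the plan.

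**What to change.** In SAP section 5.2.2:

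1. Keep the scheduled-monitor proportions, labelled as rhythm on the scheduled Holter (or imputed ECG) at the visit.
2. Add, as a supplementary summary for the single-procedure rows, cumulative freedom through the 6-month and 12-month visits with 95% CI.
3. Define failure as the first row-specific arrhythmia (AF/AT/AFL, or AF alone in the AF-only rows) after day 90 on any ECG, strip, Holter or unscheduled-visit record (more than 30 seconds on a strip or monitor), or a DCCV or repeat ablation for that arrhythmia after day 90. Carry failures forward.
4. Use actual event dates throughout. Set each landmark at the end of the visit window or at the subject's actual visit, and state which, so that in-window Holters count without re-dating.
5. Censor at the last rhythm assessment. In rows whose arrhythmia a repeat ablation did not treat, censor at that ablation and note that this may be informative.

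Protocol section 7.5 contradicts itself on repeat ablation in the first 90 days: its blanking-period text discourages it but leaves it open, while its later text confines retreatment to day 91-270. These must be reconciled before such cases are scored.

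The cost is SAP wording and one derived time-to-first-recurrence variable per arrhythmia definition, from ECG, Holter, unscheduled-visit, DCCV and retreatment data already collected. If the eCRF does not record which arrhythmia a DCCV treated, it can be linked by date to the recorded recurrence. No visit is added. The reported freedom rate may be lower, and off-schedule ECGs depend on symptoms and site practice, so the two results should be shown side by side. The timing of AAD status, visit mapping after retreatment and labelling of month-3 results are separate points and not part of this change.

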### **7.5 Recurrence of Atrial Fibrillation/Atrial Flutter/Atrial Tachycardia (AF/AFL/AT)**

#### Arrhythmia Recurrence during the Blanking Period

Occurrences of symptomatic atrial fibrillation or other (tachyarrhythmias) during the first 90 days post-ablation (blanking period) may be transient in nature and not associated with the

long-term effectiveness of the ablation treatment. However, prolonged AF should be treated as soon as possible to maintain sinus rhythm during the remodeling period. Treatment should follow the Investigator's standard of care for AF recurrence, which may include a DCCV and/or AAD administration. Repeat ablations may be considered during the blanking period; however, they are discouraged.

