#### 4.2 Analysis of Safety Objectives

##### 4.2.1 Analysis of Primary Safety Objective

Subjects who remain free from device/procedure related MAEs, as adjudicated by the CEC, that occur within the first twenty-four (24) hours post index procedure will be considered a success with respect to the primary safety objective, and subjects who experience at least one such MAE will be considered a primary safety failure. MAEs that occur during the first 24 hours will be reported and adjudicated by the CEC for any probable relationship to the device and/or procedure.

The analysis of the primary safety objective will be performed on the safety population. The number and proportion of subjects in the safety population who are primary safety successes will be computed, along with a 95% exact binomial (i.e., Clopper-Pearson) confidence interval on the proportion.

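### Repeat ablation on days 91-270 is yes/no by protocol but gets a 95% CI on the mean rather than the exact binomial interval the SAP uses for its main proportions (minor)

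*Combined protocol and SAP*

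**What the plan says.** Protocol 7.5, on recurrence beyond the blanking period: "One retreatment is allowed and may only occur in the time range from day 91 through day 270 post-ablation". For the first 90 days it says: "Repeat ablations may be considered during the blanking period; however, they are discouraged". A repeat in that earlier period lies outside the window that the SAP counts.

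SAP 5.1.2 lists the number of repeat ablation procedures on days 91-270 as a clinical outcome measure. SAP 5.2.2 (Clinical Outcome Measures) says that this number "from day 91-270 (i.e., from three months to nine months) will be summarized via mean, standard deviation, median, range" and number of non-missing responses, and adds: "A 95% CI on the mean will also be provided". The analysis population is the treatment population.

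The SAP handles three other subject-level outcomes differently:

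- Primary safety (4.2.1): number and proportion, "along with a 95% exact binomial (i.e., Clopper-Pearson) confidence interval on the proportion".
- Acute procedural success (5.2.2, Procedure Outcome Measures): "An exact binomial 95% CI on the proportion will also be provided".
- Freedom from arrhythmia (5.2.2, Clinical Outcome Measures): "along with exact binomial 95% CI's for each proportion".

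**The concern.** With one retreatment allowed, each subject's count is 0 or 1 apart from protocol deviations. The mean is then the proportion re-ablated, the SD follows from it, and the median is 0 whenever fewer than half are retreated. A normal-theory interval on that mean is symmetric, whereas the sampling distribution of a small proportion is skewed. Its upper limit therefore tends to be too low.

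SAP 2.1 says that the analyses consist of descriptive statistics and confidence intervals, with no hypothesis tests. The interval is thus the only statement of uncertainty that a reader gets about the repeat-ablation rate.

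**Working it through.** **Inputs.** At most one repeat per subject on days 91-270 (protocol 7.5). n = 125 for the combined studies (protocol 8.4, SAP 1.3). Two assumptions: the CI on the mean is a t-interval, since SAP 5.2.2 names no method; and the true repeat rate p is varied over a range, since the documents give none.

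**Step 1: the plan's own figure.** The only stated precision is for primary safety: a half-width of 3.89% at an observed 96.0%. Clopper-Pearson at 120/125 gives 90.91% to 98.69%, and (98.69 - 90.91)/2 = 3.89. It reproduces, and confirms the exact method as the plan's own standard for a proportion.

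**Step 2: limits for x repeat ablations in 125.** With p̂ = x/n, the sample variance of a 0/1 variable is n·p̂(1 - p̂)/(n - 1), so the t-interval is

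p̂ ± t(0.975; 124) × √[p̂(1 - p̂)/(n - 1)], with t = 1.979.

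Example, x = 3: 0.024 ± 1.979 × √(0.024 × 0.976/124) = 0.024 ± 1.979 × 0.01374 = -0.32% to 5.12%.

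The Clopper-Pearson limits are the 2.5% quantile of Beta(x, n - x + 1) and the 97.5% quantile of Beta(x + 1, n - x).

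| x/125 | t-interval (%) | Clopper-Pearson (%) |
|---|---|---|
| 0 | 0 to 0 | 0 to 2.91 |
| 3 | -0.32 to 5.12 | 0.50 to 6.85 |
| 4 | 0.07 to 6.33 | 0.88 to 7.99 |
| 10 | 3.18 to 12.82 | 3.90 to 14.22 |
| 25 | 12.89 to 27.11 | 13.38 to 28.09 |
| 31 | 17.12 to 32.48 | 17.51 to 33.32 |

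**Step 3: coverage and upper-side misses.** Coverage at p is the sum of Binomial(125, p) probabilities over every x whose interval contains p. The upper-side miss is the sum over every x whose upper limit is below p; its nominal value is 2.5%. Example, p = 3%: the t upper limit is 2.38% at x = 1 and 3.83% at x = 2, so it misses when x is 0 or 1. That probability is 0.97^125 + 125 × 0.03 × 0.97^124 = 0.022 + 0.086 = 10.8%.

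| True rate p | t coverage | t upper limit below p | Exact coverage |
|---|---|---|---|
| 3% | 88.7% | 10.8% (x ≤ 1) | 96.4% |
| 5% | 94.8% | 4.8% (x ≤ 2) | 96.4% |
| 10% | 92.7% | 6.0% (x ≤ 7) | 96.5% |
| 15% | 93.7% | 5.3% (x ≤ 12) | 96.8% |
| 20% | 93.8% | 4.2% (x ≤ 17) | 95.6% |
| 25% | 94.9% | 3.2% (x ≤ 22) | 96.2% |
| 30% | 94.6% | 3.7% (x ≤ 28) | 96.0% |

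The exact interval's upper-side miss stays below 2.5% at each of these rates.

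**Step 4: negative lower limits.** At n = 125 the t lower limit is negative only with 1, 2 or 3 events. The chance of that is 12% at p = 5% and 0.1% at p = 10%.

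**The case against.** The case for leaving the text alone has real substance.

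- **No method is stated.** The SAP says only that a CI on the mean will be given. The t-interval is the ordinary reading, but it is an assumption. This stands.
- **The effect depends on an unknown rate.** Total coverage is close to nominal at about 25% and above (95.1% at 35%). A reader might infer that the interval is badly wrong in general; the documents give no rate that would support this. What persists across 3-30% is the low upper limit.
- **Negative limits.** A reader might infer that impossible rates are likely. They need exactly 1-3 events, and nothing in the documents points to so few.
- **Range and median.** A reader might infer that these are useless. The one-retreatment cap is a conduct rule, protocol 11.13 foresees deviations, and the SAP pools a second study whose protocol is not among the documents. A maximum above 1 would expose a subject retreated more than once, so the range has a use.
- **Information is not lost.** The mean of a 0/1 variable is the proportion, and n is reported, so a reader could compute the exact interval. The table shells are not in the text available, so they may already show a number and percent.
- **The SAP's convention is not universal.** Rhythm and completion percentages have no stated interval. The comparison holds only for proportions given one.
- **DCCV counts.** A reader might extend the point to the cardioversion counts in the same section. Those are not capped at one, so a mean is legitimate there.

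None of this gives a reason to prefer a CI on the mean for a variable that is binary by protocol.

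**Conclusion.** The point holds as a minor one. A measure that is 0/1 by protocol is given a continuous-data summary and interval, out of line with the exact intervals specified for primary safety, acute success and freedom from arrhythmia. On the t-interval assumption at n = 125, the upper limit is about 1.0 to 1.7 percentage points lower than the exact one for 25 down to 3 events (28.1 - 27.1 = 1.0; 6.85 - 5.12 = 1.73). With no events the t-interval has no width at all. If the repeat rate turns out to be about 25% or more, the practical difference is small. The point estimate is unaffected. The measure is secondary and descriptive and is not among the objectives listed in protocol 6.2.2; no sample size, test or primary conclusion depends on it.

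**What to change.** In SAP 5.2.2, replace the CI on the mean for repeat ablations with the number and proportion of treatment-population subjects who have a repeat ablation on days 91-270, and a Clopper-Pearson 95% CI. The range may be kept to show any subject retreated more than once. The DCCV summaries need no change on this ground.

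The cost is one sentence of SAP wording and the matching table shell. No new data, sample size or conduct change is needed. The only downside is a slightly higher upper limit.
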